- *Participants will be told that the research includes completion of a particular task, when in fact, that task will not be administered.*
- *Study is designed to introduce a new procedure (or task) that participants are not initially told about.*
- *If yes, a waiver of informed consent must be requested under question IV.3.*

• No

VII.E. Project Description (E)

VII.E.1

Will subjects be randomized?

Yes

VII.E.1.a

Will any subjects be blinded to which study arm they have been assigned?

Yes

VII.E.1.b

Does the protocol permit telling subjects their treatment assignment at the end of the entire study?

Yes

VII.E.1.c

Describe the circumstances under which subjects will be told what study arm they have been assigned.

At the end of all sessions, and upon request by the subject, the participant will be informed about the stimulation condition they experienced.

VII.E.2

Describe randomization scheme/assignment including ratio such as 1:1, 2:1 etc.

The study will be a double-blind, sham-controlled, randomized parallel design. Post-COVID-19 patients with fatigue, post-COVID-19 patients without fatigue, and subjects without a history of a COVID-19 diagnosis (controls) will be randomly assigned to one of two groups. One group will

receive tDCS (tDCS Group; n = 25 in each group of subjects; 75 total) and the other group will receive SHAM (SHAM Group; n = 25 in each group of subjects; 75 total). The study will involve nine sessions at the INPL.

VII.E.3

Will any questionnaires, surveys, or written assessments be used to obtain data directly from subjects in this study?

Yes

VII.E.4

List all questionnaires, surveys, written assessments and ATTACH each one to the application.

(NOTE: You are NOT prohibited from attaching copyrighted materials to this application)

Chalder Fatigue Scale

C19-YRS-Covid-Rehab-screening-tool

Fatigue Assessment Scale (FAS)

Fatigue Severity Scale (FSS)

EQ-5D-5L Quality of Life questionnaire

Visual analog scale for pain

COVID19 Severity Survey

Pittsburgh Sleep Quality Index (PSQI) (to determine sleep quality)

International Physical Activity Questionnaire (IPAQ) (to quantify recent physical activity levels)

VII.E.5

Does this project involve creating any audiotapes, videotapes, or photographs?

No

VII.E.6

Provide a detailed description in sequential order of the study procedures following the consent process - DO NOT cut and paste from the Consent Document.

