The data that will be shared with the Medical University of South Carolina (MUSC) will be de-identified, age, race and ethnicity will be reported as required by NIH (see attached template that will be requested for reporting purposes) as part of a final report to MUSC.

X.7

Does your study meet the NIH criteria for a Certificate of Confidentiality or will you be applying for Certificate of Confidentiality?

No

XI. Data Analysis

XI.1

Describe the analysis methods you will use, including, if applicable, the variables you will analyze

The generalized estimating equation (GEE) framework will be utilized to assess changes over time in fatigue and quality of life measures. An interaction term between time and treatment will allow us to test the within- and between-treatment differences over all time points. Using histograms, variable distributions will be assessed to decide which link function to specify when modeling each outcome. To account for the inherent correlation that occurs in repeated measures data, we will cluster on subject ID. In addition to

examining the unadjusted relationship between the time-treatment interaction and each outcome, we will consider the addition of control variables, which will reduce the likelihood of unaccounted confounders. The control variables being considered for inclusion in the adjusted models are age, sex, and disease duration. For each outcome, models will be fit for all possible combinations of control variables. The predictor set that yields the smallest Akaike information criterion (AIC) will be considered the optimal control variable set to adjust associations between the main predictor and the outcomes. Statistical significance will be assessed at the $\alpha = 0.05$ level.

XI.2

Provide the rationale or power analysis to support the number of subjects proposed to complete this study.

The sample size calculation was based on the Fatigue Severity Scale data from our own preliminary data that assessed the effects of multiple sessions of 4 mA tDCS on fatigue in people with multiple sclerosis. The effect size of this difference = 0.91 (Cohen's d). With alpha fixed at 0.05, we would need 20 total subjects in each group (tDCS and SHAM; details below) to achieve 80% power in a two-tailed independent samples test. Therefore, to account for 20% data and subject attrition, we will recruit 25 subjects per group (150 total).

XII. Future Research

XII.1

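### XI.1 fixes no variance estimator or small-sample reference for the GEE; under the usual default with 20–25 subjects per arm, a nominal 5% test has a true type I error of about 6% for a single-visit contrast and 8–9% for a joint interaction test

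*Combined protocol and SAP*

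**What the plan says.** Section XI.1 states: "The generalized estimating equation (GEE) framework will be utilized to assess changes over time in fatigue and quality of life measures". Within- and between-treatment differences are to be tested through a time-by-treatment interaction covering all time points, with a link function chosen for each outcome from its histogram. On correlation it says "To account for the inherent correlation that occurs in repeated measures data, we will cluster on subject ID", and on error control "Statistical significance will be assessed at the $\alpha = 0.05$ level". The section is silent on the variance estimator, the working correlation, the reference distribution and any small-sample adjustment.

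Section XI.2 sizes the trial on an effect for which "The effect size of this difference = 0.91" and concludes that "we would need 20 total subjects in each group (tDCS and SHAM; details below) to achieve 80% power in a two-tailed independent samples test". Allowing for 20% attrition, it recruits 25 per group.

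Section VII.E.6 schedules assessments on Day 1, on Day 5, and three and six weeks after Day 5. It also ends asymptomatic subjects' participation after the first session. VI.13 and VII.E.2, by contrast, describe all three populations as randomised ("tDCS Group; n = 25 in each group of subjects; 75 total", and the same number for sham).

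**The concern.** When a GEE is clustered on subject, the customary inference uses the robust sandwich variance and compares the Wald statistic with normal or chi-square critical values. That is justified when the number of clusters is large. With 20 to 25 clusters per arm, two things go wrong in the same direction. The sandwich is biased low: with complete data it divides by n where n − 1 is needed. The reference distribution also takes no account of the variance having been estimated.

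P-values are then too small and confidence intervals too narrow for every fatigue and quality-of-life comparison, before any question of multiple outcomes arises. The comparison used to size the trial in XI.2, analysed as a t-test, would hold its 5%. The analysis in XI.1, run on defaults, would not.

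**Working it through.** **The plan's own figure.** For d = 0.91, two-sided alpha 0.05 and 80% power, the two-sample t-test (noncentral t) gives n = 19.96, so 20 per group, with power 0.801 at n = 20. Then 20 / (1 − 0.20) = 25. Both figures in XI.2 reproduce.

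**Inputs.**
- Clusters: 25 per arm recruited (XI.2, VII.E.2) and 25 × 0.80 = 20 after attrition. This is the symptomatic population only, because VII.E.6 follows no one else.
- Visits: four (VII.E.6), so a categorical time-by-treatment interaction has 3 df.
- Alpha: 0.05 (XI.1).
- Assumed, because XI.1 does not say: uncorrected sandwich, normal or chi-square reference. For the exact results, also identity link, complete normal data, equal arms and no covariates.

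**Form of the statistic.** In this setting the interaction estimates are the between-arm differences in mean change. The sandwich variance is the usual sample variance multiplied by (n − 1)/n. The Wald statistic is therefore t² × n/(n − 1) for one contrast and Hotelling T² × n/(n − 1) for the joint test. The null rejection rates follow exactly:

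- Single visit, between arms: P(|t with 2n − 2 df| > 1.96 × √((n − 1)/n)). At n = 20 the threshold is 1.96 × √0.95 = 1.910.
- Within arm: the same threshold, with n − 1 df.
- Joint 3-df test: P(F(3, 2n − 4) > 7.815 × (n − 1)/n × (2n − 4)/(3(2n − 2))). At n = 20 the threshold is 7.815 × 0.95 × 36/114 = 2.344; at n = 25 it is 7.815 × 0.96 × 46/144 = 2.397.

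| Test at nominal 5% | n = 20 per arm | n = 25 per arm | n = 75 per arm |
|---|---|---|---|
| Single visit, between arms | 6.4% | 6.1% | 5.3% |
| Within arm | 7.1% | 6.7% | – |
| Joint 3-df interaction | 8.9% | 8.0% | 5.9% |

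The last column applies only if all three populations were followed and pooled.

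**Does it depend on complete normal data?** Simulation with 10,000 replicates per scenario, 25 per arm and 20% dropout gave 8.0–8.4% for the joint test across exchangeable and AR(1) correlation and skewed errors. The Day 5 contrast gave 5.9–6.4%.

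**Does it depend on the variance estimator?** Yes. With an exchangeable working correlation and model-based variance (40,000 trials, complete data), the joint test rejected 4.6–5.3% of the time when the true correlation was exchangeable and 6.1–6.4% under AR(1). Under AR(1), single-visit rates ran from about 2% to 11%.

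**Candidate corrections, joint test.** In the balanced case the Mancl-DeRouen statistic is T² × (n − 1)/n.

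| Variance and reference | n = 20 | n = 25 |
|---|---|---|
| m/(m − 1) multiplier (m = total clusters), chi-square | 8.3% | 7.6% |
| Mancl-DeRouen, chi-square | 6.7% | 6.3% |
| Kauermann-Carroll, F(3, clusters − 2) | 6.0% | 5.8% |
| Mancl-DeRouen, F(3, clusters − 2) | 5.1% | 5.1% |

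Across the 10,000-replicate scenarios at 20–25 per arm, with and without dropout, the last option gave 4.5–5.2%. A smaller run of 1,000 replicates with the correlation estimated gave 4.5–6.5%, with a Monte Carlo standard error of about 0.7 points (√(0.05 × 0.95/1000)).

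**The case against.** The strongest reply is that XI.1 never mentions a robust sandwich or a chi-square reference. That is correct: both are assumptions about what software would do by default. A reader might infer that the written plan has an 8–9% type I error. The documents do not support that. Another variance estimator gives other rates, as the model-based results show. What stands is that the plan leaves the choice open, the usual choice is anti-conservative at this size, and the model-based alternative is unreliable when the working correlation is wrong.

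Second, 8–9% belongs only to a joint test with categorical time. XI.1 does not say that time is categorical or that the test is joint, and the hypotheses in I.5 are tied to particular visits: after five sessions, then at three and six weeks. For those contrasts the inflation is to about 6%. This also stands, and both figures have to be given.

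Third, VI.13 and VII.E.2 describe 75 per arm, which would nearly remove the problem. But VII.E.6 gives the other subjects no treatment and no follow-up, so 25 per arm is the better-supported count. The conflict between those sections should be reconciled.

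Finally, sizing a repeated-measures analysis with a two-sample test is a common simplification. A reader might infer from the mismatch with XI.1 that the sample size is wrong. It is not: 20 and 25 both reproduce.

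**Conclusion.** The concern holds as a specification gap with a measurable consequence. If XI.1 is carried out with the uncorrected sandwich and normal or chi-square critical values on 20–25 subjects per arm, the true type I error at nominal 5% is 6.1–6.4% for a single-visit between-arm contrast, 6.7–7.1% within an arm and 8.0–8.9% for a joint categorical-time interaction. The exact values assume complete normal data and an identity link; simulation with dropout and skewed errors gave similar between-arm rates. They exclude the effects of covariate selection by AIC and of testing several outcomes.

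The inflation is modest for the visit-specific hypotheses and material for a joint test. It should be corrected, but it does not undermine the design or the sample size.

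**What to change.** Keep GEE and its outcome-specific link in XI.1, and prespecify three things before treatment-group results are seen: the working correlation; a bias-corrected sandwich, preferably Mancl-DeRouen; and t or F reference distributions, for example with clusters minus 2 denominator degrees of freedom. Both the variance correction and the reference distribution are needed. State also whether time is categorical and whether the interaction is tested jointly or visit by visit.

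For outcomes modelled with an identity link, a mixed model for repeated measures with REML and Kenward-Roger degrees of freedom is an acceptable alternative. It was not simulated here, and it would not carry over the plan's choice of link for other outcomes.

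The cost is a sentence or two and a software option, with no change to recruitment or visits. Intervals widen slightly. For a single-visit contrast, Mancl-DeRouen with t in place of the default multiplies the width by (2.024/1.960) × (20/19) = 1.09 at n = 20, or (2.011/1.960) × (25/24) = 1.07 at n = 25. Such contrasts then sit just under 5%: at n = 20, P(|t with 38 df| > 2.024 × √(20/19)) = 4.5%.

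### Adding age, sex and disease duration to the XI.1 model without covariate-by-time terms does little or nothing to the time-by-treatment effect, so it gives that effect no real protection against chance imbalance

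*Combined protocol and SAP*

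**What the plan says.** Section XI.1 plans a GEE clustered on subject. Its key sentence is: "An interaction term between time and treatment will allow us to test the within- and between-treatment differences over all time points". The plan looks first at the unadjusted interaction and then moves to adjusted models, with this purpose: "we will consider the addition of control variables, which will reduce the likelihood of unaccounted confounders". The candidates are listed: "The control variables being considered for inclusion in the adjusted models are age, sex, and disease duration". Every subset of the three is fitted for each outcome, and the subset with the smallest AIC is kept.

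Time by treatment is the only interaction named. The link is to be chosen for each outcome from histograms, and the working correlation is not stated. Under VII.E.6 the assessments are Day 1, Day 5, and three and six weeks after Day 5. XI.2 allows for attrition: "to account for 20% data and subject attrition, we will recruit 25 subjects per group". VII.E.7 says that subjects lost to follow-up will not be recontacted.

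**The concern.** A covariate that does not vary within a subject, entered as a main effect, shifts all of that subject's visits equally. The interaction compares change from Day 1 between arms, and an equal shift cancels out of change. The adjusted model can then return the same answer as the unadjusted one on the term it is meant to adjust.

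This matters because the arms are small. VI.13 requires only more than 30 days since diagnosis, with no upper limit, so disease duration may vary widely. The randomisation described in VII.E.2 mentions no stratification by it. If duration predicts recovery, and the arms differ in duration by chance, the difference in spontaneous recovery stays in the adjusted tDCS effect. Any precision that a predictor of change could offer is also lost.

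**Working it through.** **1. The plan's own figure.** Inputs from XI.2: d = 0.91, two-sided alpha 0.05, 80% power, 20% attrition. The normal approximation gives n = 2(1.96 + 0.84)²/0.91² ≈ 19 per group. The t test has power 0.779 at 19 and 0.801 at 20, so 20 per group. Then 20/0.80 = 25. The stated sample size reproduces.

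**2. Why main effects cancel.** Let A be the arm and X the fixed covariates. With an identity link the ordinary reading of XI.1 is

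E(Y at visit t) = α + β_t + γA + δ_t·A + θX.

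Subtracting Day 1 (where β and δ are zero) leaves β_t + δ_t·A. The term θX is gone. With complete data the estimate of δ_t is the between-arm difference in mean change, whatever X is. Every covariate subset then gives the same δ_t, so the AIC selection cannot alter it.

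**3. Numerical check.** GEE, 25 per arm, 4 visits, complete data, identity link, independence and exchangeable working correlation: the interaction estimates agree to within 1e-15 with and without the three covariates, and the robust standard errors are the same. With Poisson-log the point estimates also agree.

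**4. Where the equality fails.** Simulated mean absolute shift in the interaction after main-effect adjustment (25 data sets per setting; about 20% dropout related to duration):

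| Setting | Mean shift | Typical SE |
|---|---|---|
| Identity, dropout, independence | 0.088 | 0.317 |
| Identity, dropout, exchangeable | 0.031 | 0.288 |
| Gamma-log, complete | 0.077 | 0.181 |
| Logit, complete | 0.139 | 0.756 |

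**5. Do those shifts correct an imbalance?** Simulation with no true effect, 25 per arm, 200 replicates. Assumed: 0.5 SD imbalance in duration and a duration-change correlation of 0.4. On this simulation's scale the expected uncorrected bias is about 0.17. Mean false effect at week 6:

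| Setting | Unadjusted | Main effects | Covariate-by-follow-up |
|---|---|---|---|
| Complete, independence | 0.153 | 0.153 | -0.013 |
| Random dropout, independence | 0.182 | 0.180 | 0.005 |
| Random dropout, exchangeable | 0.137 | 0.137 | -0.025 |
| Duration-related dropout, independence | 0.103 | 0.135 | -0.027 |
| Duration-related dropout, exchangeable | 0.165 | 0.170 | 0.021 |
| Gamma-log, complete (log scale) | 0.059 | 0.058 | 0.006 |

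The Monte Carlo SE is about 0.02 (0.006 for gamma-log). The logit runs were too noisy to support a conclusion.

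**6. Size.** With change in SD units, bias = imbalance × correlation: 0.5 × 0.3 = 0.15, 0.5 × 0.4 = 0.20, 0.5 × 0.5 = 0.25. If the planned d is on the same scale, 0.20/0.91 = 22% of it.

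**7. Chance of such an imbalance.** P = 2[1 − Φ(0.5/√(2/n))]. For n = 25: 0.5/0.283 = 1.77, so 7.7%. For n = 20: 0.5/0.316 = 1.58, so 11.4%.

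**8. Precision.** At 20 per arm and d = 0.91, taken on the change scale, letting duration act on change gives simulated power of about 82%, 86% and 89% for correlations of 0.3, 0.4 and 0.5. Main effects leave it at about 80%.

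**The case against.** A reader might infer that the adjusted effect always equals the unadjusted one and that adjustment removes nothing. The documents do not support that. The link is left open, and 20% attrition without recontact makes incomplete series the expected case, so in any single trial the two estimates will usually differ. XI.1 also uses the model for between-arm differences at each visit, which are treatment plus interaction. Main effects do act there: the mean shift was 0.230 in complete data with an identity link. These limits on scope stand.

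XI.1 does not state the covariate form, so reading it as main effects only is an inference. It is the ordinary reading, since one interaction is named and the covariates are simply added. Silence is not a prohibition, however, and the gap is one of specification.

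A reader might also infer that the trial is biased. It is not: the arms are randomised, and the interaction is unbiased over randomisation (a check without imposed imbalance gave -0.015, Monte Carlo SE 0.015). The false effect needs both an unlucky allocation and a duration-change correlation that the documents do not give. Nor do they say that agreement between adjusted and unadjusted results will be presented as robustness.

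What the objection does not answer is step 5: where the estimates do shift under dropout or a gamma-log link, on average the shift does not remove the imbalance.

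**Conclusion.** The point holds within stated limits. Covariates entered only as main effects leave the time-by-treatment estimate and its robust standard error exactly unchanged with complete data and an identity link. They change it without correcting it, on average, under the dropout patterns and the gamma-log model examined. The purpose XI.1 gives for adjustment is therefore not met for the interaction, although it can be for single-visit differences.

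The planned sample size and its 80% power are unaffected. The exposure is a residual false effect of about 0.15 to 0.25 SD in the roughly 8 to 11% of allocations with an imbalance of 0.5 SD or more (taking 0.5 SD as the reference size), plus a forgone gain in power. Both figures rest on an assumed correlation of 0.3 to 0.5 between duration and change. If duration does not predict change, nothing is lost. This is a worthwhile, inexpensive improvement to the plan and does not invalidate it.

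**What to change.** In XI.1, for the adjusted models of the time-by-treatment effect, pre-specify disease duration as a main effect plus its interaction with a post-baseline indicator (one common term for Day 5, week 3 and week 6). Treat age and sex the same way if they are wanted. Fix this set in advance for the outcomes concerned, and state the link and working correlation.

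Use disease duration only in the post-COVID groups. VI.13 and VII.E.2 also randomise controls with no COVID-19 history, for whom it is undefined.

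Do not describe a main-effects-only model as adjusting the interaction for confounding.

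The change needs wording and a few model terms, and no new data. The downside is one parameter per covariate. If a covariate does not predict change, the variance of the treatment effect rises by about 1 to 3% for each one.

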Describe study populations separately if they will be participating in different procedures - include CONTROL population if applicable.

DESCRIBE:

- **What subjects will be asked to do/what happens in the study (in sequential order)**
- **The time period over which procedures will occur**
- **The time commitment for the subject for individual visits/procedures**
- **Long-term followup and how it occurs**

Symptomatic subjects will be asked to complete 7 lab study sessions. The first lab session will take approximately 3.5 hours, the fifth lab session will take approximately 2 hours, and the tDCS sessions will take approximately 30 minutes. In all, full participation will take approximately seven weeks, with three week breaks between Lab Sessions 5, 6, and 7. Asymptomatic subjects will be asked to complete 1 lab study session, lasting approximately 2 hours.

Vascular study: In the initial session (Day 1) all subjects will 1) be consented, 2) undergo a blood draw to evaluate interleukin-6 values, lipids, glucose and c-reactive protein, complete 3) pulse wave velocity testing (arterial stiffness); 4) carotid compliance/stiffness with ultrasound 5) brachial artery flow-mediated dilation (vascular endothelial function) 6) the Fatigue Assessment Scale (FAS), 7) the Fatigue Severity Scale (FSS), 8) the visual analog scale (VAS) for pain, 9) cognitive testing 10) 1-100 symptom scale, 11) international physical activity questionnaire (IPAQ), 12) Pittsburgh sleep quality index (PSQI), and 13) the 6-minute walk test. For asymptomatic participants, this will mark the end of their study participation. For symptomatic participants, they will then have their first round of the intervention receiving either sham or tDCS.

The following four days will include receiving either 20 min of tDCS or sham treatment, depending on group randomization. Day 5 will include the same testing battery (blood draw, PET scan in 10 subjects from each group [i.e., those that got the pre scan], questionnaires, fatigue testing, walking test) as Day 1, except the subjects will not repeat the MRI scan, strength testing, or receive tDCS.

LONG-TERM EFFECTS OF tDCS: Three- and six-weeks following Day 5, participants will repeat the testing battery conducted on Days 1 and 5.

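### XI.1 does not use the Day 1 score as a covariate, so its time-by-treatment test is generally less precise than a baseline-adjusted comparison of the same data

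*Combined protocol and SAP*

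**What the plan says.** XI.1 analyses fatigue and quality of life with GEE clustered on subject. The test of interest is described so: "An interaction term between time and treatment will allow us to test the within- and between-treatment differences over all time points". For the adjusted models: "The control variables being considered for inclusion in the adjusted models are age, sex, and disease duration". The subset is chosen by the smallest AIC. The Day 1 value of the outcome is not among the candidates, and no constraint of equal arm means at Day 1 is stated. XI.1 names no working correlation, and leaves the link to be chosen from histograms.

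VII.E.6 itemises the Day 1 battery, which includes "6) the Fatigue Assessment Scale (FAS), 7) the Fatigue Severity Scale (FSS". For symptomatic subjects it comes before the first stimulation. The battery is repeated on Day 5 and three and six weeks later. The same section ends asymptomatic subjects' participation after Day 1, so the longitudinal comparison rests on the symptomatic arms.

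XI.2 sizes the trial on FSS data: "The effect size of this difference = 0.91 (Cohen's d". It continues: "With alpha fixed at 0.05, we would need 20 total subjects in each group", and "to achieve 80% power in a two-tailed independent samples test". It does not say whether 0.91 is in SDs of the score or of the change. Nor does it mention baseline adjustment or a correlation.

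**The concern.** The Day 1 score is usually the strongest predictor of a later score on the same scale. On the ordinary reading of XI.1 it enters only by subtraction. Subtraction fixes the weight on baseline at 1, whereas regression estimates it. When the true slope is below 1, a chance baseline difference between arms is over-corrected. With 20 per arm, such a difference has a standard error of sqrt(2/20) = 0.32 SD.

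The listed covariates do not make up for this. Age, sex and disease duration do not vary over the study. As main effects with complete data and an identity link, they cancel out of a within-subject change. In a simulated data set, adding them left the interaction estimate (-0.8749) and its standard error (0.4634) unchanged.

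At stake is precision in a small trial whose planned power, 80%, leaves no margin.

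**Working it through.** **Inputs from XI.2:** d = 0.91, two-sided alpha 0.05, 80% power, 20 evaluable per arm, 20% attrition. **Assumptions, not in the documents:** rho between Day 1 and follow-up, and equal SDs at both times.

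**1. The plan's own figure.** For a two-sample t-test with 20 per arm, the noncentrality is 0.91 × sqrt(20/2) = 2.88 on 38 df, which gives power 80.1%. The exact requirement is 19.96, so 20 per arm. Then 20/(1 − 0.2) = 25, and 6 × 25 = 150. The stated sample size reproduces.

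**2. What the planned test estimates.** A GEE with categorical time, treatment and their interaction (identity link) was fitted to complete simulated data with 20 per arm and four visits. The first interaction term was -0.4346 under both independence and exchangeable working correlation. The arm difference in mean change from Day 1 was also -0.4346.

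**3. Variances.** In units of 2 × SD²/n, the change contrast has variance 2(1 − rho). The baseline-adjusted contrast has 1 − rho² in large samples, so the ratio is (1 + rho)/2. Estimating the slope multiplies the adjusted variance, on average under normality, by 1 + 1/(38 − 2) = 37/36.

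| rho | change | adjusted | ratio | ratio × 37/36 |
|---|---|---|---|---|
| 0.3 | 1.4 | 0.91 | 0.65 | 0.67 |
| 0.5 | 1.0 | 0.75 | 0.75 | 0.77 |
| 0.7 | 0.6 | 0.51 | 0.85 | 0.87 |
| 0.9 | 0.2 | 0.19 | 0.95 | 0.98 |
| 0.95 | 0.1 | 0.0975 | 0.975 | 1.00 |
| 0.98 | 0.04 | 0.0396 | 0.99 | 1.02 |

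Simulation at 20 per arm gave 0.67, 0.76, 0.87, 0.98, 1.00 and 1.03. Break-even is where (1 + rho)/2 = 36/37, that is, rho = 0.946.

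**4. Power at 20 per arm, d in change-score SDs.** The planned test has 80.1% at every rho. The adjusted effect is 0.91/sqrt((1 + rho)/2) = 1.13, 1.05, 0.99 and 0.93 at rho 0.3, 0.5, 0.7 and 0.9. Power is 94%, 90%, 86% and 82%, or 93%, 89%, 85% and 81% after slope estimation.

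**5. Power at 20 per arm, d in score SDs.** The planned effect is 0.91/sqrt(2(1 − rho)) = 0.77, 0.91 and 1.17 at rho 0.3, 0.5 and 0.7, with power 66%, 80% and 95%. Adjusted power is 84%, 90% and 98%, or 83%, 89% and 97% after slope estimation.

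**6. The common-baseline alternative.** Under working independence, a GEE that forces equal arm means at Day 1 reduces to the raw follow-up difference, with variance factor 1. That is worse than 2(1 − rho) whenever rho exceeds 0.5.

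**The case against.** The sponsor could say that baseline is not ignored: on the reading above, each subject's Day 1 value is in the contrast, by differencing. That stands. A reader might infer that the comparison is biased or invalid; it is not, because randomisation protects the change contrast too.

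The reading itself is inferred. XI.1 does not say that time is categorical, that treatment has its own main effect, or that the link is identity. With continuous time or another link, the interaction is not an arithmetic change score and the formulas above do not apply as written. This limits confidence in the size of the loss. It does not alter the absence of the Day 1 score from the covariate list.

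Rho may also be high, since Day 5 follows Day 1 by only four days. At 0.9 the gain is about 2%, and from about 0.95 there is none, so it would be wrong to say that adjustment wins at every rho below 1. Equal SDs matter as well. If the follow-up SD were 1.3 times the baseline SD, the large-sample ratios would be 0.81, 0.91 and 0.99 at rho 0.3, 0.5 and 0.7. With a smaller follow-up SD (0.8 times), the gain would be larger. These points bound the benefit but do not remove the case for adjustment, because its worst cost in the range examined is 2% to 3% of variance.

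**Conclusion.** The point holds as one of efficiency. XI.1 omits the Day 1 score as a covariate. Under the ordinary reading, equal SDs and 20 per arm, this forgoes about a third of the variance at rho 0.3, a quarter at 0.5, an eighth at 0.7 and almost nothing at 0.9. Rho is an assumption throughout.

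A reader might go further and conclude that the trial is underpowered or its sample size wrong. The documents do not support that. The planned test falls below 80% only if d = 0.91 is in score SDs and rho is below 0.5, and neither fact is given. If d is in change-score SDs, the planned power is 80.1%, as stated. The change is worth making because power has no margin and, for the two fatigue scales, the data are already in the Day 1 schedule.

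**What to change.** In XI.1, take the Day 5, week-3 and week-6 values as the outcomes. Force the Day 1 value of the same outcome, and its interaction with visit, into every model, outside the AIC selection. Report the adjusted tDCS-minus-sham difference at each visit.

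A model with a common Day 1 mean in both arms is an acceptable alternative only if it is likelihood-based with unstructured covariance. It should not be a GEE with working independence, for the reason in step 6.

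Confirm that EQ-5D-5L is completed on Day 1. VII.E.4 lists it among the questionnaires, but the itemised Day 1 battery in VII.E.6 does not include it. In XI.2, state which SD underlies 0.91 and, if the preliminary data allow, the correlation.

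The cost is a short rewrite of XI.1 and a few degrees of freedom. FAS and FSS need no new data.
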